**Period 2**

- Allow study drug interruption up to 7 consecutive days for AEs and emergency surgery during Week 16 to Week 24 in Period 2, and after Week 24 until Week 64/PD, up to 30 consecutive days of study drug interruption is allowed.
- If the subject undergoes elective surgery, the study drug should be interrupted 1 week prior to the planned surgery. Allow reintroduction of study drug once the physician has examined the surgical site and determined that it has healed and there is no sign of infection.
- If the subject must undergo emergency surgery, the study drug should be interrupted at the time of surgery. Allow reintroduction of study drug once the physician has examined the surgical site and determined that it has healed and there is no sign of infection.

The Investigator should contact the AbbVie TA MD if a subject experiences a study drug interruption > 7 consecutive days during Weeks 1 through 24 or > 30 consecutive days after Week 24 to discuss the management of the subject and possible discontinuation from participation in the study.

**6.1.8 Data Monitoring Committee**

An external DMC will review unblinded safety data. See Section [5.5.5.2](#) for details.

**6.1.9 Cardiovascular Adjudication Committee**

An independent committee of physician experts in cardiovascular adjudication will be utilized to assess potential cardiovascular AEs in a blinded manner as defined by the Cardiovascular Adjudication Committee charter.

**6.2                   Product Complaint****6.2.1               Definition**

A Product Complaint is any Complaint (see Section [6.0](#) for the definition) related to the biologic or drug component of the product.

For a product this may include, but is not limited to, damaged/broken product or packaging, product appearance whose color/markings do not match the labeling, labeling discrepancies/inadequacies in the labeling/instructions (example: printing illegible), missing components/product, or packaging issues.

Any information available to help in the determination of causality to the events outlined directly above should be captured.

**6.2.2               Reporting**

Product Complaints concerning the investigational product must be reported to the Sponsor within 1 business day of the study site's knowledge of the event via the Product Complaint form. Product Complaints occurring during the study will be followed-up to a satisfactory conclusion. All follow-up information is to be reported to the Sponsor (or an authorized representative) and documented in source as required by the Sponsor. Product Complaints associated with adverse events will be reported in the study summary. All other complaints will be monitored on an ongoing basis.

Product Complaints may require return of the product with the alleged complaint condition. In instances where a return is requested, every effort should be made by the Investigator to return the product within 30 days. If returns cannot be accommodated within 30 days, the site will need to provide justification and an estimated date of return.

The description of the complaint is important for AbbVie in order to enable AbbVie to investigate and determine if any corrective actions are required.

---

**8.0 Statistical Methods and Determination of Sample Size****8.1 Statistical and Analytical Plans**

The primary analysis will be conducted after all subjects have completed Period 1 (Week 12).

Completed and specific details of the statistical analysis will be described and fully documented in the Statistical Analysis Plan (SAP). The SAP will be finalized prior to the database lock for the analysis at the end of Period 1. The statistical analyses will be performed using SAS (SAS Institute Inc., Cary, NC, USA).

**8.1.1 Analysis Populations****8.1.1.1 Full Analysis Set (FAS)**

The Full Analysis Set (FAS) includes all randomized subjects who received at least one dose of study drug. The FAS will be used for all efficacy and baseline analyses.

**8.1.1.2 Per Protocol Analysis Set**

The Per-Protocol Analysis Set represents a subset of the FAS and consists of all FAS subjects who did not meet any major protocol violations during the study. Definitions of major protocol violations will be detailed in the SAP. Additional analysis may be conducted on the Per Protocol analysis set, in order to evaluate the impact of major protocol violations.

**8.1.1.3 Safety Analysis Set**

The Safety Analysis Set consists of all subjects who received at least one dose of study drug. For the Safety Analysis Set, subjects are assigned to a treatment group based on the treatment actually received, regardless of the treatment randomized.

**8.1.2      Subject Accountability, Disposition and Study Drug Exposure****8.1.2.1      Subject Accountability**

The following will be summarized by site and by treatment group as well as overall, separately for Period 1 and Period 2: number of subjects randomized, the number of subjects who received at least one dose of study drug, the number of subjects who completed, and the number of subjects who prematurely discontinued.

**8.1.2.2      Subject Disposition**

Separately for Period 1 and Period 2, the number and percentage of subjects who are randomized, received at least one dose of study drug, prematurely discontinued and completed will be summarized by treatment group and overall. Reasons for premature discontinuation will be summarized separately for all randomized subjects by treatment group and overall, with frequencies and percentages by reason for discontinuation.

**8.1.2.3      Study Drug Exposure**

Exposure to study drug will be summarized for the Safety Analysis Set for Period 1 alone as well as for Period 1 and Period 2 combined. The exposure to study drug (days) will be summarized with the mean, standard deviation, median, and range for each treatment group. The exposure to study drug is defined as the difference between the dates of the first and last doses of the study drug plus 1 day.

Study drug compliance will be summarized for each treatment group. The compliance is defined as the number of tablets taken (i.e., the difference between the number of tablets dispensed and the number of tablets returned) during the subject's participation divided by the number of tablets a subject is supposed to take each day times the length of time that the subject was in the Treatment Phase.

**8.1.3****Analysis of Demographic and Baseline Characteristics**

Demographic and baseline characteristics will be summarized by treatment group and overall for the FAS. For the purpose of this analysis, baseline data for each subject will be the data collected immediately prior to the first dose of study drug in Period 1.

Summary statistics for continuous variables will include the number of observations, mean, standard deviation, median, and range. For discrete variables, frequencies and percentages for each category will be summarized.

Medical history will be presented by counts and percentages of subjects, broken down by Body System and Diagnosis.

Prior therapy and medication will be summarized by treatment group. Prior therapy and medication will include all therapies and medications with a start date prior to the date of first dose of study drug.

Concomitant medications will also be summarized with frequencies and percentages for each treatment group. All medications administered during study drug exposure will be included.

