**Main Exclusion:**

1. Prior exposure to any Janus kinase (JAK) inhibitor (including but not limited to tofacitinib, baricitinib, and filgotinib).
2. Subjects who are considered inadequate responders (lack of efficacy) to bDMARD therapy as determined by the Investigator.
3. History of any arthritis with onset prior to age 17 years or current diagnosis of inflammatory joint disease other than RA (including but not limited to gout, systemic lupus erythematosus, psoriatic arthritis, axial spondyloarthritis including ankylosing spondylitis and non-radiographic axial spondyloarthritis, reactive arthritis, overlap connective tissue diseases, scleroderma, polymyositis, dermatomyositis, fibromyalgia [currently with active symptoms]). Current diagnosis of secondary Sjogren's Syndrome is permitted.
4. Laboratory values meeting the following criteria within the Screening period prior to the first dose of study drug: serum aspartate transaminase  $> 2 \times$  upper limit of normal (ULN); serum alanine transaminase  $> 2 \times$  ULN; estimated glomerular filtration rate by simplified 4-variable Modification of Diet in Renal Disease formula  $< 40 \text{ mL/min}/1.73 \text{ m}^2$ ; total white blood cell count  $< 2,500/\mu\text{L}$ ; absolute neutrophil count  $< 1,500/\mu\text{L}$ ; platelet count  $< 100,000/\mu\text{L}$ ; absolute lymphocyte count  $< 800/\mu\text{L}$ ; and hemoglobin  $< 10 \text{ g/dL}$ .

**Investigational Product:** Upadacitinib**Dose:** 15 mg QD**Mode of Administration:** Oral**Reference Therapy:** Matching placebo for upadacitinib QD**Dose:** N/A**Mode of Administration:** Oral**Duration of Treatment:** Period 1: 12 weeks; Period 2: up to 52 weeks**Criteria for Evaluation:****Efficacy:****Period 1**

The primary endpoint in Period 1 is the proportion of subjects achieving ACR20 response at Week 12. ACR20 response rate will be determined based on 20% or greater improvement in Tender Joint Count (TJC) and Swollen Joint Count (SJC) and  $\geq 3$  of the 5 measures of Patient's Assessment of Pain (Visual Analog Scale [VAS]), Patient's Global Assessment of Disease Activity (VAS), Physician's Global Assessment of Disease Activity (VAS), Health Assessment Questionnaire Disability Index (HAQ-DI), or hsCRP.

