Subjects with prior exposure to at most one bDMARD for RA may be enrolled in the study (up to 20% of total number of subjects) after the required washout period is satisfied **and if** they have limited exposure to bDMARD (< 3 months) OR response to bDMARD but had to discontinue that bDMARD due to intolerance (regardless of treatment duration) (for washout periods, see Inclusion Criterion 7, Section 5.2.1). Subjects who are

considered bDMARD inadequate responders (lack of efficacy), as determined by the Investigator, are not eligible.

[figure not shown]
At Week 24, if a subject fails to meet the Low Disease Activity (LDA) criterion (LDA defined as  $\text{CDAI} \leq 10$ ) the investigator should adjust the subject's background RA therapies. Starting at Week 24 (after Week 24 assessments have been performed), initiation of or change in corticosteroids, non-steroidal anti-inflammatory drugs (NSAIDs), acetaminophen, or adding or increasing doses of csDMARDs (concomitant use of up to 2 csDMARDs except the combination of MTX and leflunomide) is allowed as per local label. Starting at Week 24, at least 20% improvement in BOTH TJC AND SJC compared to baseline is required to remain in the study. Anyone who does not fulfill this criterion at 2 consecutive visits (starting at Week 24) (see Section 5.2.3.1) must be discontinued from the study.

Subjects taking MTX should take oral folic acid throughout study participation. Folic acid dosing and timing of regimen will be based on the Investigator's discretion.

Subjects who complete the Week 12 visit (end of Period 1) will enter the open-label 52-week extension portion of the study, Period 2. Subjects who are assigned to upadacitinib treatment in Period 1 will continue to receive upadacitinib per original randomization assignment in an open-label manner. Subjects who are assigned to placebo in Period 1 will be switched to receive open-label upadacitinib from Week 12 onwards.

The primary analysis will be conducted after all subjects have completed Period 1 (Week 12) or have prematurely discontinued prior to Week 12. Study sites and subjects will remain blinded to the treatment assignment in Period 1 for the duration of the study.

Schematics of Period 1 and Period 2 are shown in [Figure 1](#).

**Figure 1.** Study Design

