6.3 Prior Treatment and Concomitant Medications

Prior and concomitant medications will be summarized by each randomized treatment group as well as overall for FAS. Prior medications are those medications taken prior to the first dose of study drug. This includes medications with a start date before the first study drug administration date, regardless of the end date of these medications.

Medications taken on the day of the first dose of study drug are not counted as prior medications. Concomitant medications are those medications, other than study drug, taken after the first dose of study drug and within 1 day of the last dose of study drug. This includes medications with a start date between first study drug administration and last study drug administration + 1 day, as well as, medications with a start date prior to first dose of study drug and which are ongoing after first dose of study drug. Medications taken on the day of the first dose of study drug are counted as concomitant medications.

The number and percentage of subjects who received a prior medication and the number and percentage of subjects who received a concomitant medication will be tabulated separately by the generic name assigned by the most current version of the World Health Organization (WHO) Drug Dictionary.

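### The concomitant-medication table runs to the last dose of study drug under the randomized arm, so it cannot show co-medication by arm in the controlled 12 weeks

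*Protocol*

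**What the plan says.** Protocol 8.1.3 summarizes concomitant medications for each treatment group, without saying how groups are formed after the switch, and adds: "All medications administered during study drug exposure will be included". SAP 6.3 supplies the columns: "Prior and concomitant medications will be summarized by each randomized treatment group as well as overall for FAS". It also supplies the window, which covers medications "taken after the first dose of study drug and within 1 day of the last dose of study drug", together with "medications with a start date prior to first dose of study drug and which are ongoing after first dose of study drug". The unit of the table is the subject: "the number and percentage of subjects who received a concomitant medication will be tabulated separately by the generic name".

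The design sections say what happens to the placebo arm over that window. Protocol 5.1: "Subjects who are assigned to placebo in Period 1 will be switched to receive open-label upadacitinib from Week 12 onwards". The synopsis gives the treatment durations as "Period 1: 12 weeks; Period 2: up to 52 weeks".

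Nearby summaries do name the period. Protocol 8.1.2.2 opens its disposition summary with "Separately for Period 1 and Period 2, the number and percentage of subjects". Protocol 8.1.2.3 gives exposure for Period 1 alone and for both periods combined, and SAP 8.2 limits compliance to Period 1. SAP 6.3 makes no such split.

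**The concern.** The ACR20 comparison at Week 12 is made on background therapy that is meant to be stable. Protocol 5.2.3.1 holds csDMARD doses steady up to Week 24 apart from reductions for safety, and does not allow NSAIDs, acetaminophen or corticosteroids to be newly started before then, with limited exceptions. From Week 24 the same section lets these therapies, low-potency analgesics and csDMARDs be started or changed. A single table that runs to the last dose puts a start at Week 6 and a start at Week 30 in the same cell.

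This matters for interpretation because the non-responder rules in SAP 9.1.2 and 9.4.1 act on missing data and on discontinuation of study drug, not on changes in co-medication. A subject who starts an analgesic or a steroid during Period 1 can still count as a responder. Whether that happened to a similar extent in both arms is a question a reader would take to the concomitant-medication table, and as specified the table cannot answer it.

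**Working it through.** The plan attaches no figure to this table, so there is none to reproduce. The check is a reading of the window, a calculation of time shares, and a comparison with the other planned outputs.

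**1. Is open-label upadacitinib study drug?** Yes.
- SAP 7.0 counts subjects who stop study drug during Period 2.
- SAP 8.1 includes the upadacitinib exposure of subjects switched from placebo in its summary of exposure to study drug.
- SAP 10.3.3.2 notes that the first upadacitinib dose may be later than the first dose of study drug.

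So the last dose of study drug for a placebo-randomized completer falls at about Week 64, and the SAP 6.3 window stays open until then. The column label stays the randomized arm throughout.

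**2. Time shares for a completer.** Inputs: Period 1 is 12 weeks and Period 2 is 52 weeks (Protocol synopsis), 12 + 52 = 64 in total.
- On placebo: 12/64 = 19%.
- On upadacitinib: 52/64 = 81%.
- After Week 24: (64 − 24)/64 = 40/64 = 62.5%.

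If 10% of the arm finish Period 1 but never enter Period 2 (an assumption that borrows the dropout figure in SAP 4.3), the upadacitinib share for the arm is 0.9 × 52/(12 + 0.9 × 52) = 46.8/58.8 = 80%.

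**3. Time share at the Week 12 analysis.** SAP 4.4 places this analysis after the last subject has finished or left Period 1. It states no data cut at each subject's own Week 12, and SAP 7.0 provides for subjects still ongoing in Period 2. With m the mean number of Period 2 weeks accrued by then, the share is m/(12 + m). The documents give no accrual period, so m is an assumption:

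| m (weeks) | Share on upadacitinib |
|---|---|
| 0 | 0% |
| 6 | 6/18 = 33% |
| 12 | 12/24 = 50% |
| 26 | 26/38 = 68% |
| 52 | 52/64 = 81% |

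**4. Do other planned outputs give the Period 1 picture?**
- SAP 6.1: csDMARD category, oral steroid use and dose, and MTX dose by arm, at baseline only.
- SAP 6.3, prior medications: everything started before first dose, by randomized arm. This covers baseline NSAIDs but nothing started later.
- SAP 9.3: absence of corticosteroid use by visit, including Weeks 1 to 12, by randomized sequence, but only among baseline users.
- SAP 6.4: use of excluded or prohibited medication, summarized and listed by treatment group, with no period stated.
- SAP 5.1 and 9.2.2: a Per Protocol rerun of the primary endpoint that removes subjects with major Period 1 deviations. This tests their effect on the result but does not describe co-medication.

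Some Period 1 changes are permitted and so need not appear as deviations: as-needed use, reductions for safety, and substitution within a class after a tolerability problem (Protocol 5.2.3.1). None of the five outputs tabulates RA medications started or permissibly changed in Period 1 by arm.

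**The case against.** The table is descriptive and has no test attached. Many of the Period 1 starts that would worry a reader are protocol departures, so SAP 6.4 should pick them up by treatment group, and the Per Protocol rerun checks whether major ones move the primary result. Baseline therapy is shown by arm. Differences in medication started after randomization may themselves reflect treatment response, so they are not a clean balance check. Start and stop dates are recorded (Protocol 5.2.3), so a Period 1 table could be produced at any time. All of this stands, and it limits the weight of the point. It does not fill the gap, because permitted changes are not deviations and SAP 6.4 names no period.

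Three stronger readings are tempting and are not supported:

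- A reader might infer from the 81% that the placebo column consists mostly of medication taken on upadacitinib. The table counts subjects per generic name, not weeks. Background csDMARDs, and NSAIDs or steroids continued from baseline, enter the column on Day 1, while the subject is on placebo.
- A reader might infer that the pooled table will show a false imbalance or reverse a real one. That would depend on rates of starting medication in each period and arm, which the documents do not give. SAP 6.3 also plans no row for newly started RA medication.
- A reader might take Protocol 8.1.3 alone to fix the randomized-arm columns. It refers only to treatment group. The columns and the exact window come from SAP 6.3.

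**Conclusion.** The point holds as a limitation of one descriptive table. As SAP 6.3 is written, medications first taken on open-label upadacitinib appear under placebo, and co-medication by arm in the controlled 12 weeks cannot be read from the table. The 81% describes planned time for a completer at study end. At the Week 12 analysis the share could lie anywhere from near 0% to near 81%, depending on accrual. Baseline, steroid, deviation and Per Protocol outputs cover part of what is missing. The CMH test of ACR20, the alpha and the power do not draw on this table and are unaffected. It is a cheap improvement to reporting and does not threaten the primary conclusion.

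**What to change.** In SAP 6.3, with a matching sentence in Protocol 8.1.3, define concomitant medication by period:

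- **Period 1:** from the first dose of study drug to before the first Period 2 dose, or to the last dose plus 1 day for subjects who do not enter Period 2. Summarize by randomized arm, and show RA medications started after the first dose separately from those ongoing at baseline. Report this table with the primary analysis.
- **Period 2:** from the first Period 2 dose, summarized by treatment sequence (upadacitinib throughout; placebo then upadacitinib), as SAP 9.1.1 already does for long-term efficacy.

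No new data are needed. Start and end dates are collected, and the first Period 2 dose date already bounds the analysis windows in SAP 5.2. The cost is a few lines of text and one extra run of a descriptive table. A table by generic name will still not show dose reductions in a continuing drug. If those are wanted by arm, they need a separate row or listing from the dosage data that Protocol 5.2.3 requires.

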**8.1.4****Efficacy Analysis**

All efficacy analyses will be carried out using the FAS population, which includes all randomized subjects who receive at least one dose of study drug.

**8.1.4.1****Efficacy Analysis for Period 1****8.1.4.1.1****Primary Efficacy Variables**

The primary endpoint in Period 1 (at Week 12) is the proportion of subjects achieving ACR20 response at Week 12.

Analysis of the primary endpoint will be conducted on the FAS based on treatment as randomized. Comparison of the primary endpoint will be made between the upadacitinib

group and the placebo group using the Cochran-Mantel-Haenszel test adjusting for main stratification factors. For the primary analysis, Non-Responder Imputation (NRI) will be used.

The analysis will be repeated using Observed Cases (OC). Supportive analysis will also be conducted on the Per Protocol Analysis Set.

The primary efficacy analyses will also be performed in demographic subgroups including age, gender, weight, body mass index, race, and country to assess the consistency of the treatment effect. Additional subgroup analyses based on baseline disease characteristics and stratification factors will also be conducted.

#### **8.1.4.1.2 Key Secondary Efficacy Variables**

Key secondary endpoints are listed in Section [5.3.3.1.2](#).

For binary endpoints, frequencies and percentages will be reported for each treatment group. Similar analyses as for the primary endpoint will be conducted.

For continuous endpoints, the mean, standard deviation, median, and range will be reported for each treatment group. Comparison for the upadacitinib treatment group and the placebo group will be carried out using the analysis of covariance model with treatment group as the fixed factor, and the corresponding baseline value and the main stratification factors as the covariates.

See Section [8.1.4.1.5](#) for imputation methods.

